6.4.1 AT lowering and peak thrombin

Correlation between AT (actual AT activity and AT lowering) and peak TG will be computed on paired assessments, where both parameters are measured on the same day. Log transformation may be used.

6.5 ANALYSES DURING DOSE INTERRUPTION

For participants who had clinical hold in 2017, the following exploratory analyses will be performed:

Rate of AT recovery since last dose before interruption will be summarized descriptively. AT activity over time since last dose before interruption will be plotted.

AT activity and peak TG over time since last dose before interruption will be plotted.

ABR before, during and after the interruption period will be summarized descriptively. Similarly, maximum bleed free duration for treated bleeding events before and after interruption period will be summarized descriptively. ABR and maximum bleed free duration before and after the interruption period will be analyzed based on efficacy period and on-treatment strategy considering all intercurrent events. Bleeding events during the first 29 days after dose resumption will not be considered based on on-treatment strategy for participants whose 2017 dose hold period >84 days as outlined in [Section 6.3](#). ABR during the interruption period will consider intercurrent events II – V based on on-treatment strategy. The interruption period will start from 29 days after last dose before interruption till the day before first dose at resumption of treatment.

ABR before, during and after the interruption period will be summarized descriptively. Similarly, maximum bleed free duration for all bleeding events before and after interruption period will be summarized descriptively. ABR and maximum bleed free duration before and after the interruption period will be analyzed based on efficacy period and on-treatment strategy considering all intercurrent events. Bleeding events during the first 29 days after dose resumption

will not be considered based on on-treatment strategy for participants whose 2017 dose hold period >84 days as outlined in [Section 6.3](#). ABR during the interruption period will consider intercurrent events II – V based on on-treatment strategy. The interruption period will start from 29 days after last dose before interruption till the day before first dose at resumption of treatment.

For participant who had voluntary dose pause interruption in 2020, similar analysis will be done for the AT/TG assessments, ABR and maximum bleed free duration.

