10.2.3 Efficacy Analyses

Annualized bleed rate estimate will be calculated as the number of bleed events occurring 4 weeks after the first dose of fitusiran in this study and until the End of Study visit. Bleed-free duration will be defined as the maximum time intervals between 2 bleeding events and will be analyzed descriptively. Bleed rate reduction and percentage reduction compared with pretreatment will also be calculated.

A weight-adjusted consumption of FVIII or FIX or BPA will be assessed.

Patient-reported QoL will be assessed by descriptive statistics for the EQ-5D-5L questionnaire. Descriptive statistics will be provided for observed values and changes from baseline (ie, Day 1, predose in the current study).

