- Onset period: The onset period is defined as the period of time consisting of the first 28 days: Treatment Day 1 to Treatment Day 28 (of TDR14767(ALN-AT3SC-001) and LTE14762) (see above - definition of “Treatment Day”); this is the period of time during which the AT lowering capacity of fitusiran is increasing but has not yet reached therapeutic levels.
- Efficacy period 1: The efficacy period 1 is defined as Treatment Day 29 to earlier of End of study date before the dose pause or the last fitusiran administration date before the dose pause + 28 days, whichever comes first.
- Treatment period 1: The treatment period 1 is defined to be the onset period plus the efficacy period 1.

The revised dose and regimen:

- Dose adjustment period: The dose adjustment period is defined as the dose re-start Day 1 to the earlier of dose re-start Day 168 or the end of study.
- Efficacy period 2: The efficacy period 2 is defined as the dose re-start Day 169 to the end of study visit
- Treatment period 2: The treatment period 2 is defined to be the dose adjustment period plus the efficacy period 2.

All the analysis periods will exclude the period of following intercurrent events to avoid confounding of treatment effect for the primary efficacy analysis based on On-Treatment Strategy:

Intercurrent events:

I. “Dose interruption periods”:

- a. Gap between TDR14767(ALN-AT3SC-001)/ LTE14762 study >28 days and skips at least two doses in the gap: Exclude events occurring on dates starting from the date of the last dose in 001 +29 days to the date of first dose in LTE14762 +28 days and gap duration >84 days.
- b. Clinical hold/dose pause period during LTE14762 study: Exclude events occurring on dates starting from the date of the last dose before dose interruption +29 days to the date of dose resumption +28 days and on-hold duration > 84 days.
 - Dose hold in 2017: The last dose before dose interruption is defined as the last fitusiran administration before 2017 [REDACTED]. The first dose after dose resumption is defined as the first fitusiran administration after 2017 [REDACTED].
 - Voluntary dose pause in 2020: The last dose before dose interruption is defined as the last fitusiran administration before 2020 [REDACTED]. The first dose after dose resumption is defined as the first fitusiran administration after 2021 [REDACTED].

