6.3.1.2 Bleed-free duration

Bleed-free duration (BFD) for each participant will be calculated as the time interval between 2 protocol-defined treated bleeding events, excluding bleeding events that occur during the intercurrent periods during both of the efficacy periods based on on-treatment strategy respectively. If participant don’t have any bleeding event in each of the efficacy period, the overall duration of the corresponding efficacy period will be the bleed-free duration. ABR and maximum BFD (after 1st significant dose) will be summarized descriptively. A similar calculation

of bleed-free duration considering all bleeding events will be performed for clinical hold or voluntary dose pause analysis described in [Section 6.5](#).

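### Maximum bleed-free duration depends on how long a participant is observed, so rows set side by side for periods of unequal length cannot show whether bleeding changed

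*SAP*

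**What the plan says.** Protocol 10.2.3 fixes the statistic: "Bleed-free duration will be defined as the maximum time intervals between 2 bleeding events and will be analyzed descriptively".

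SAP 6.3.1.2 applies it within each efficacy period under the on-treatment strategy. Bleed-free duration (BFD) is "calculated as the time interval between 2 protocol-defined treated bleeding events", and the maximum is summarised. For a participant with no bleed, "the overall duration of the corresponding efficacy period will be the bleed-free duration". A participant with exactly one bleed is not addressed.

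SAP 6.5 puts this maximum before and after the 2017 clinical hold, once for treated bleeds and once for all bleeds. For treated bleeds, "maximum bleed free duration for treated bleeding events before and after interruption period will be summarized descriptively". The basis is the same in both cases: "ABR and maximum bleed free duration before and after the interruption period will be analyzed based on efficacy period and on-treatment strategy". For the 2020 pause, "similar analysis will be done for the AT/TG assessments, ABR and maximum bleed free duration".

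SAP 6.3 defines the periods. For the original regimen: "The efficacy period 1 is defined as Treatment Day 29 to earlier of End of study date before the dose pause", or 28 days after the last dose before the pause if that comes first. Efficacy period 2 runs from re-start Day 169 to the end-of-study visit. Neither 6.3.1.2 nor 6.5 sets a common window, scales to observed time, or censors.

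**The concern.** The longest of several gaps tends to be longer when there is more time in which gaps can occur, and for a bleed-free participant the value is the period length itself. If the two periods being set side by side differ in length, the rows can differ although the bleeding rate has not moved.

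A before/after table is read as a comparison even when no test is attached. Time between bleeds is a listed efficacy endpoint (SAP 3.2.1), and Amendment 9 extended follow-up so that the revised regimen could be assessed. The ABR in the same paragraphs of SAP 6.5 is divided by days at risk and the maximum BFD is not, so the two could disagree with nothing in the output to explain why.

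**Working it through.** The documents give no figure for maximum BFD, so there is none to reproduce. The check has two parts: period lengths from the documents' dates, then the behaviour of the SAP rule at a constant rate.

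**Period lengths**

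- *Before the 2017 hold.* First enrolment 08-Oct-2015 (SAP 2.5) to the 01-Sep-2017 anchor (SAP Table 4) is 694 days. Less the 28-day onset period: 694 - 28 = 666. This is a ceiling for those first significantly dosed in the extension. The parent study's last visit was 20 July 2017 (SAP 2.1), so late roll-overs first dosed in the extension have only weeks.
- *After the hold, to 31-Oct-2020 (SAP Table 4).* 1,156 days, less the hold, less 28 days after resumption. The resumption date is redacted. Assuming a hold of 84 to 270 days: 1,156 - 84 - 28 = 1,044, down to 1,156 - 270 - 28 = 858.
- *All of efficacy period 1, same participants.* 666 + 858 = 1,524 to 666 + 1,044 = 1,710 days, or more than four years.
- *Efficacy period 2.* At the 18-month minimum (Protocol Table 3, footnote a): 548 - 168 = 380 days. A late roll-over followed for 72 months: 20-Jul-2017 plus six years is 20-Jul-2023, which is 905 days after 26-Jan-2021 (SAP Table 4). 905 - 168 = 737, so up to about 750.

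SAP 6.5 does not say whether "before" the 2020 pause means all of efficacy period 1 or only the part after the 2017 hold. On either reading the lengths are generally unequal.

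**The SAP rule at a constant rate**

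Assumptions: bleeds follow a Poisson process with an unchanging rate, and the ABR values are chosen because the documents give none. Literal rule: no bleeds gives the period length, two or more gives the longest gap between bleeds, one gives no value.

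Simulated **mean** maximum BFD in days:

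| ABR | 380 d | 666 d | 1,000 d | 1,460 d |
|---|---|---|---|---|
| 0.5 | 345 | 509 | 596 | 690 |
| 1 | 270 | 330 | 405 | 525 |
| 2 | 173 | 246 | 332 | 427 |

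The mean rises along every row. It also rises at ABR 5 (128, 184, 221 for the first three lengths). With gamma-distributed rates between participants (shape 1) at ABR 2, it is 235, 332 and 421. At constant ABR 2, the contrast of 666 with 1,000 days is 332/246 = 1.35, and that of 380 with 1,460 days is 427/173 = 2.47, with no change in bleeding.

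Simulated **median** in days:

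| ABR | Period length: median |
|---|---|
| 0.5 | 730: 730; 1,040: 541 |
| 1 | 380: 380; 666: 282; 1,000: 355; 1,460: 484 |
| 2 | 380: 148; 666: 223; 1,000: 306; 1,460: 397 |
| 4 | 380: 125; 730: 198; 1,040: 238; 1,460: 274 |

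The median rises at ABR 2 and 4 but not at 1 or below. The reason can be checked by hand. At ABR 1 over 380 days the expected count is 380/365.25 = 1.04. Then P(0) = 0.353, P(1) = 0.368 and P(2 or more) = 0.279. Among participants with a defined value, 0.353/(0.353 + 0.279) = 56% have no bleeds, so the median is exactly 380. Over 666 days the count is 1.82, P(0) = 0.161 and P(2 or more) = 0.544. The bleed-free share falls to 0.161/0.705 = 23%, and the median drops to a gap between bleeds.

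**Equal windows**

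With the same length and the same rate the two distributions are identical by construction. Simulated over 380 days in both periods (here also counting the gaps at the start and end of the window), the medians were 316 and 313 at ABR 1, 233 and 233 at ABR 2, and 150 and 150 at ABR 5.

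**The case against.** The strongest defence is that nothing rests on these rows. SAP 6.5 calls the hold analyses exploratory and summarises them descriptively, and SAP 5.2 analyses the two regimens separately. No test or claim is attached to maximum BFD. The ABR stands beside it, and SAP 6.3.1.1 adds ABR by year for treatment period 1 and every 6 months for treatment period 2. The protocol itself prescribes the maximum, and SAP 2.6 records that Kaplan-Meier analyses were removed because the protocol asks only for description. All of this stands, and it lowers the severity. It does not make the unequal-period rows interpretable.

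A reader might infer that the 2017 rows must look like improvement and the 2020 rows like loss of effect, by some fixed percentage. The documents do not support that. They give no bleeding rate, the resumption date is redacted, and follow-up differs by participant. At ABR 0.5 the simulated median is 559 days over 1,000 days and 750 over 750 days, so the shorter, later period would look better. At ABR 2 the same pair gives 308 and 246, about 20% shorter. A large contrast such as 1,460 against 380 days pairs a long original-regimen period with the minimum follow-up after re-start.

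**Conclusion.** The point holds as a limit on interpretation. Maximum BFD under SAP 6.3.1.2 is a function of period length as well as bleeding rate, and SAP 6.5 sets it side by side for periods that differ in length. These rows therefore cannot show whether bleeding changed across an interruption or between regimens. The ABR can.

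The size is illustrative. It rests on assumed ABRs, a constant-rate Poisson model, an assumed hold of 84 to 270 days, and period lengths that are ceilings or minima rather than individual data. The rise in the mean was seen at every rate tried. For medians, even the direction depends on the rate. The SAP also leaves open whether a gap may span an excluded intercurrent period, which would change individual values.

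It would go too far to read this as a false-positive risk or as a threat to the trial's conclusions. No test is planned on this measure, and neither the primary safety objective nor the primary ABR analysis uses it. Severity: minor.

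**What to change.** In SAP 6.5, and wherever original and revised regimens appear side by side, compute maximum BFD for the comparison over equal-length on-treatment windows. One choice is the last 12 months before each interruption and the first 12 months of the efficacy period after it, in participants who have both. Keep the full-period, protocol-defined maximum as a listing, with each participant's observation time next to it. This stays descriptive, keeps the protocol's definition, and does not reopen the removal of Kaplan-Meier analyses.

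In the same edit, state what value a participant with one bleed receives and whether a gap may cross an excluded period.

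The cost is SAP wording and one re-derived table. Some follow-up goes unused in the windowed comparison, and late roll-overs with only weeks before the 2017 hold drop out of that contrast. At the 18-month minimum the 12-month window leaves 380 - 365 = 15 days of slack, so the SAP should also name a shorter common window for use if many participants fall below 12 on-treatment months.

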5.2 CONCOMITANT MEDICATIONS

Use of concomitant medications will be recorded on the patient's eCRF as specified in the Schedule of Assessments (Table 1, Table 2 and Table 3). This includes all prescription medications, herbal preparations, over-the-counter medications, vitamins, and minerals. Any changes in medications during the study will also be recorded on the eCRF.

Treatment for hemophilia must be "on demand." Importantly, patients should not use factor concentrates as prophylaxis for bleeding episode prevention, including doses related to anticipated hemostatic challenges such as physical activity, after Day 7 on fitusiran. For prophylaxis of bleeding episodes in patients who require major operative procedures see Section 5.7.

Concomitant use of drugs known to prolong the OT/OTc interval should be avoided.

Antifibrinolytics may be used as single agents but may not be used in combination with factor or BPA. Use of FEIBA and rFVIIa as combination therapy is not recommended. Use of emicizumab (Hemlibra®) during the study is not permitted.

a Study drug may be provided in prefilled syringes either at the clinic (healthcare setting) or in a nonhealth care setting (home injection) in a subset of patients receiving 80 mg monthly dose of fitusiran. The patient will be trained on prefilled syringe self-administration. Patients who have missed more than 6 consecutive fitusiran doses for any reason should utilize the study drug provided as a vial and syringe for at least 3 injections prior to utilizing prefilled syringe.

If patients use NSAIDs intermittently or chronically, they must have been able to tolerate them with no previous side effects (eg, gastric distress or bleeding).

Use of >4 g acetaminophen per day is not permitted.

For patients with known HCV infection, concurrent treatment with ribavirin or interferon is not permitted during fitusiran treatment. In patients without cirrhosis or HBV-coinfection, concurrent treatment of HCV with direct-acting antiviral (DAA) therapy may be permitted after review and approval of the individual treatment plan by the study Medical Monitor.

Treatment for HIV is permitted and must be recorded as concomitant medication.

Standard vitamins and topical medications are permitted. However, topical steroids must not be applied anywhere near the injection site(s) unless medically indicated.

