5.3 MANAGEMENT OF BLEEDING EPISODES WITH FACTOR OR BYPASSING AGENTS WHILE ON FITUSIRAN

Investigators will establish and provide instructions for an individualized bleed management plan based on the guidelines in Table 8 for each patient.

The bleed management plan should be reviewed by the Investigator or designee with the patient at each dosing (and via telephone contact every 2 weeks [±4 days] between fitusiran dosing) and updated as necessary.

Initiation of fitusiran treatment results in a progressive lowering of AT levels over 4 weeks.

Guidelines are provided below for patients newly initiating therapy or re-initiating therapy, and during continuous therapy with fitusiran.

Bleed management guidelines for patients with AT recovery of ≥60% prior to re-initiation of fitusiran or during a potential fitusiran dose pause

AT recovery is defined as AT activity level of approximately 60% or greater (per the central laboratory).

After initiating therapy with fitusiran, it is recommended that patients call the Investigator prior to dosing with factor or BPA, and must call for any repeat doses of FVIII, FIX, aPCC, or for the third or subsequent dose of rFVIIa.

As quickly as 7 days after the initial fitusiran dose, the majority of patients will have AT levels at or below 60% residual activity. By 14 days after dosing, it is expected that 94% of participants will have AT activity lowering of >50%, with a median value of 66.8%. Based on these AT kinetics, it is recommended that patients continue with their standard factor/BPA regimens for the first week following re-initiation of fitusiran dosing, with institution of the protocol-specific bleed management guidelines with reduced factor/BPA starting the second week after re-initiation, as described below and in Table 8.

During the study period, in case fitusiran is on pause for any reason and AT activity levels return to approximately 60% (per the central laboratory), patients can initiate regular factor concentrates or BPAs for prophylaxis therapy to prevent spontaneous bleeding episodes, per Investigator discretion in consultation with the study Medical Monitor.

Bleed management guidelines for Week 2 and beyond, and for patients with AT recovery of <60% prior to re-initiation of fitusiran:

When a patient experiences symptoms that may be consistent with bleeding episodes, the following steps should be followed:

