4 PARTICIPANT POPULATION

The following populations/analysis sets may be evaluated and used for presentation of the data.

Safety analysis set 1: All participants who receive at least a partial dose of study drug during the LTE14762 study under the original dose and regimen (ie, before the 2020 voluntary dose pause). The analysis set will be the main analysis set for analysis under original dose and regimen except for efficacy analysis and pharmacodynamics analysis.

Safety analysis set 2: All participants who receive at least a partial dose of study drug during the LTE14762 study under the revised dose and regimen (ie, after the 2020 voluntary dose pause). The analysis set will be used in safety analysis under revised dose and regimen. The analysis set will be the main analysis set for analysis under revised dose and regimen except for efficacy analysis and pharmacodynamics analysis.

Full analysis set 1: All participants in safety analysis set 1. The analysis set will be used in efficacy analysis and pharmacodynamics analysis under original dose and regimen.

Full analysis set 2: All participants in safety analysis set 2. The analysis set will be used in efficacy analysis and pharmacodynamics analysis under revised dose and regimen.

Per protocol set 1: All participants in the safety analysis set 1 who have no major protocol violations under the original dose and regimen in the following categories

- Failure to meet key eligibility criteria, which will be identified prior to database lock
- Prophylactic use of factor treatment or BPA (except for prophylaxis of bleeding in patients who require procedures or surgeries)

The protocol violation will be manually reviewed and adjudicated prior to database lock.

Per protocol set 2: All participants in the safety analysis set 2 who have no major protocol violations under the revised dose and regimen in the following categories

- Failure to meet key eligibility criteria, which will be identified prior to database lock
- Prophylactic use of factor treatment or BPA(except for prophylaxis of bleeding in patients who require procedures or surgeries)

The protocol violation will be manually reviewed and adjudicated prior to database lock.

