5.2 GENERAL METHODS

Both efficacy and safety analysis under the original and revised dose regimens will be analyzed separately, unless otherwise specified. The data collected during the 2020 voluntary dose pause will be analyzed along with the pre-pause data.

A significant dose is defined as any single dose of fitusiran that is greater than or equal to 20 mg. Before the voluntary dose pause, the analysis period for efficacy endpoints starts from the date of first significant dose up to the earlier of 2020 voluntary dose pause date or the last day of study follow-up. For safety endpoints, the analysis will be performed based on LTE14762 study period data only up until the dose restart date. Date of first significant dose in the TDR14767(ALN-AT3SC-001) and LTE14762 study/studies will be designated as Treatment Day 1; there will be no Treatment Day 0. Participants who receive doses (either weight-dependent or weight-independent) of at least 20 mg but less than 75 mg will be “classified” as “50 mg” participants, while participants receiving doses of greater than or equal to 75 mg will be “classified” as “80 mg” participants (except PK analysis in which actual dose on Day of PK sample collection will be used). However, for purposes of efficacy and safety analyses and summaries in the final CSR report for the LTE14762 study, the classification of each participant under the original dose and regimen will be according to the fixed dose to which they are eventually taken by the end of the LTE14762 study original dose period. For example, participants who received a 50 mg dose in TDR14767(ALN-AT3SC-001) or LTE14762 and then were switched to 80 mg dose at some point in time during the LTE14762 study, are classified in the LTE14762 study as “80 mg” participants (except for PK analyses). Treatment after the volunteer dose pause will be treated as each participant’s treatment sequence.

[figure not shown]
Treatment Days under the original dose and regimen will be calculated as evaluation date – first significant dose date +1 and pre-treatment days will be calculated as evaluation date – first significant dose date. (The pre-treatment day formula applies when evaluation date < first significant dose date; ie, for example, there will be pre-treatment Days ... -3, -2, -1, then treatment Day 1, 2, 3, 4, ...; there is no “pre-Treatment Day 0” nor is there any “Treatment Day 0”).

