- c. Missing two consecutive doses in LTE14762 (eg, a participant skips at least two consecutive scheduled doses): If participant under Q2M regimen before the dose interruption, then exclude events occurring on dates starting from the date of the last dose before the dose interruption + 57 days to the date of the dose resumption + 56 days. If participant under QM regimen before the dose interruption, then excluded events from the date of the last dose before the dose interruption + 29 days to the date of the dose resumption + 28 days. The missing two consecutive doses will be considered separately before and after the dose pause in 2020.
- d. Fitusiran treatment discontinuation in LTE14762: Exclude events occurring on any dates starting from the date of the last dose +29 days if the last dose regimen is QM (ie, until the end of the study.) If the last dose regimen is Q2M, then the start date of this intercurrent event should be last dose + 57 days.

II. Perioperative period of major surgery and major trauma is defined as the day of the surgery or trauma through the final day on which supplemental hemostatic or antithrombotic treatments are administered as part of the perioperative treatment plan.

III. Perioperative period of minor surgery is defined as the perioperative period of surgery as defined for major surgery (see above) or to 72 hours from the end of surgery, whichever is later.

IV. Period of antithrombin treatment defined as the first day of antithrombin treatment through the final day on which antithrombin or other anticoagulant therapies are administered +5 half-lives.

V. After treatment with emicizumab.

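### SAP 6.5 keeps days on regular factor/BPA prophylaxis in the during-interruption ABR by default, so if anyone used it that rate is not like-for-like with the before and after rates

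*SAP*

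**What the plan says.** SAP 6.5 plans an exploratory, descriptive summary of ABR before, during and after the 2017 clinical hold, for treated bleeds and for all bleeds, and a similar analysis for the 2020 voluntary pause. The before and after rates use the efficacy period and apply every intercurrent event. For the middle period the rule is "ABR during the interruption period will consider intercurrent events II – V based on on-treatment strategy".

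SAP 6.3 defines those four events: the perioperative period of major surgery (and major trauma), the perioperative period of minor surgery, antithrombin treatment plus a washout, and the time described as "After treatment with emicizumab". Regular factor or BPA prophylaxis is not among them, nor in any part of event I.

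The protocol treats prophylaxis differently on and off fitusiran. Under Protocol 5.2 treatment is on demand, and after Day 7 on fitusiran "patients should not use factor concentrates as prophylaxis for bleeding episode prevention". Under Protocol 5.3, if fitusiran is paused and AT has returned to about 60%, "patients can initiate regular factor concentrates or BPAs for prophylaxis therapy to prevent spontaneous bleeding episodes", at the investigator's discretion and in consultation with the Medical Monitor.

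The SAP mentions factor/BPA prophylaxis in one rule only. Section 4 makes its non-surgical use a major violation for the per protocol sets and adds that "The protocol violation will be manually reviewed and adjudicated prior to database lock".

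**The concern.** SAP 2.6 gives the purpose of 6.5 as evaluating AT recovery and bleeding during the two interruptions. A reader will naturally take the during rate as what happens to bleeding when fitusiran is withdrawn, and compare it with the rates on either side.

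That comparison is clean only if background treatment is the same in all three periods. By protocol it need not be: on-demand treatment before and after, with prophylaxis possible in between. The SAP removes time after emicizumab, which is also a bleed-preventing treatment, but leaves factor or BPA prophylaxis days in both numerator and denominator. If prophylaxis works as intended, the middle rate is pulled down and the contrast shrinks, and nothing in the reported figure would show it.

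**Working it through.** The plan gives no figure to reproduce. The check is mainly a comparison of passages.

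1. **Days counted.** The 6.5 window runs from 29 days after the last dose to the day before resumption. SAP 6.3.1.1 computes, per participant, ABR = bleeds / days in the period × 365.25.

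2. **Days removed.** Only events II–V. A day on regular prophylaxis therefore stays in.

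3. **Can such days occur in the window?** Protocol 5.3 permits them, with limits. SAP 2.5 dates the pause sentence to Amendment 9 (23 Jun 2021). That is after the 2017 hold and 148 days after 26 Jan 2021, the 2020-pause end anchor in SAP Table 4. The stated reason is clarity, and the earlier pause rule is not given. Under Protocol 6.5.1.3 restart is possible from AT ≥22%, so some patients may never reach 60%. Protocol 5.3 also says, for patients with recovered AT, that "it is recommended that patients continue with their standard factor/BPA regimens for the first week following re-initiation of fitusiran dosing". This suggests that background regimens were foreseen around the restart. It does not prove prophylaxis in the window: that week follows resumption, and a standard regimen may be on-demand.

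4. **Does another rule catch it?** The per protocol exclusion drops whole participants, not days. SAP 6.3.1.1 applies it to the primary ABR analyses, and 6.5 does not call for it. SAP 6.3.3 summarizes consumption per bleed and per injection. The concomitant-medication tables in 6.8.7 are not tied to interruption days.

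5. **Direction and possible size.** Let *f* be the share of window days on prophylaxis and *r* the ratio of the bleeding rate on prophylaxis to that off it, both rates constant. Then
   - ABR(unsplit) = ABR(off) × [(1 − *f*) + *f* × *r*]
   - shortfall against the prophylaxis-free rate = *f* × (1 − *r*)

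   The documents give neither *f* nor *r*. With *f* = 0 the shortfall is 0. Over assumed ranges *f* = 0.25 to 0.75 and *r* = 0.1 to 0.5, it runs from 0.25 × 0.5 = 12.5% to 0.75 × 0.9 = 67.5%. For example, with 20/year off, 6/year on and *f* = 0.5, the unsplit rate is 0.5 × 20 + 0.5 × 6 = 13.0/year. These figures illustrate the mechanism; they are not estimates.

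6. **Is the primary ABR touched?** Efficacy period 1 ends no later than 28 days after the last pre-pause dose, and efficacy period 2 starts at restart Day 169. The 2020 window lies in neither. The 2017 hold falls within the span of efficacy period 1, but event I.b removes it when it lasts more than 84 days.

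7. **How short can the window be?** The 2020 dates in SAP 6.3 are redacted, so I assume those in Table 4. The latest last dose is 30 Oct 2020 and the earliest restart 27 Jan 2021. The window is then 28 Nov 2020 to 26 Jan 2021, or 60 days. One bleed moves a participant's ABR by 365.25 / 60 = 6.1/year. This says nothing about the mixing; it shows how unstable individual rates become once days are taken out.

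**The case against.** The strongest reply is that 6.5 does contain a rule. It names the events that modify the rate and fixes the window, so everything else is included, much as in the treatment policy analysis elsewhere in the SAP. The stated aim is bleeding during the pause, which can mean bleeding as it happened. On that reading the rate understates nothing. This stands: a reader might infer that the SAP simply forgot the issue or has no rule, but the text supports only an implicit inclusion rule. What remains is that the inclusion is not stated, and that the same rule takes out emicizumab time.

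A second reply is that use is unproven. That also stands. No passage reports prophylaxis in either interruption, the explicit permission is dated after the Table 4 anchor, and eligible days may be few or none.

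A third is that listings already give visibility. Diaries record factor and BPA doses (Protocol 8.1), and all study data are listed by patient (Protocol 10.2). A diligent reader could find users, but not the effect on this ABR.

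A fourth concerns remedies. Splitting each interruption into pooled on- and off-prophylaxis rates would give a statistic unlike the per-participant before and after ABRs. Because permission depends on AT recovery, the split would also largely track AT level and could not isolate a prophylaxis effect. With at most 48 patients enrolled, the strata would be small. This is why the fix below is narrower.

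**Conclusion.** The point holds in a limited form. By default, days on regular non-surgical factor/BPA prophylaxis remain in the during-interruption ABR, although the protocol permits such prophylaxis in a pause and bars factor prophylaxis on fitusiran. If anyone used it, the rate mixes two background treatments and is not like-for-like with its comparators.

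The size is unknown and is zero if there was no use; no percentage bias is claimed. The downward direction rests on prophylaxis reducing bleeding, and on the reader wanting the rate without fitusiran or prophylaxis.

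A reader might infer that the main efficacy result is compromised. The documents do not support that: 6.5 is exploratory and descriptive, and the primary on-treatment ABR is not affected by the 2020 pause. This is a change worth considering, held with medium confidence.

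**What to change.** In SAP 6.5 only, with no new intercurrent event in 6.3:

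- Keep the planned during-interruption ABR and state that prophylaxis days are included.
- Report, separately for 2017 and 2020, the number of participants on regular non-surgical factor/BPA prophylaxis and their person-days on it. If there were none, one sentence saying so is enough.
- If there are users, add one descriptive sensitivity during-interruption ABR that leaves out prophylaxis days, as is done for emicizumab time. Use the same statistic before, during and after; if pooled bleeds over pooled person-time is chosen because of the short windows, compute it for all three periods.
- Note that the remaining days are weighted to earlier, lower-AT time and that heavier bleeders may start prophylaxis first, so the rate is descriptive only.

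The cost is SAP wording, modest programming and extra review. The review planned before database lock adjudicates violations by participant. It would also have to record start, stop and purpose of prophylaxis on pause days, and keep permitted pause use apart from per protocol violations. That separation needs care because SAP 5.2 says "The data collected during the 2020 voluntary dose pause will be analyzed along with the pre-pause data", which could bring permitted pause use under per protocol set 1.

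The sensitivity rate will be imprecise. With assumed counts, 5 bleeds in 1 patient-year gives 5.0/year (exact Poisson 95% CI 1.6 to 11.7), and 20 bleeds in 4 patient-years gives 5.0/year (3.1 to 7.7). Overdispersion would widen both.
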